1. INTRODUCTION

The purpose of this reporting and analysis plan (RAP) is to describe the analyses to be included in the Clinical Study Report for Protocol HZA114971:

Revision Chronology:		
2016N269987_00	28-JUN-2016	Original
2016N269987_01	04-NOV-2016	Amendment 1
2016N269987_02	06-MAR-2019	Amendment 2

Note that in line with the guidelines, this RAP will use the term “participant” (except Section 11.9: List of Data Displays), while all data displays (Tables, Figures & Listings) produced as part of the planned dry-run and the Statistical Analysis Complete (SAC), will use the term “subject” which reflects GSK Data Display Standards terminology.

2. SUMMARY OF KEY PROTOCOL INFORMATION

2.1. Changes to the Protocol Defined Statistical Analysis Plan

Changes from the originally planned statistical analysis specified in the protocol amendment 2 (Dated: 06/MAR/2019) are outlined in [Table 1](#).

Table 1 Changes to Protocol Defined Analysis Plan

[figure not shown]
Protocol	Reporting & Analysis Plan	
Statistical Analysis Plan	Statistical Analysis Plan	Rationale for Changes

Section 9.4.1.1: Additional supportive analyses will be provided for the following subsets of the Growth Population:
 
 1. Excluding subjects who exhibit greater than or equal to Tanner Stage 2 characteristics at any point during the treatment period or follow-up period 2. Excluding subjects who have questionable height measurements (definition of questionable measurements will be provided in the RAP) 3. Excluding subjects who have height measurements taken after receiving rescue systemic corticosteroids during the treatment period 4. Excluding subjects who have height measurements taken after receiving rescue inhaled and/or 	
Section 7: Additional supportive analyses will be provided:
 
 1. Excluding participants who exhibit greater than or equal to Tanner Stage 2 characteristics at any point during the treatment period or follow-up period 2. Excluding questionable height measurements (definition of questionable measurements is provided in Section 11.6.3) 3. Excluding height measurements taken after participant receiving rescue systemic corticosteroids during the treatment period 4. Excluding height measurements taken after participant receiving rescue inhaled and/or intranasal and/or systemic corticosteroids during the treatment period 	
This is to clarify that the intention in the protocol was to exclude from the supportive analyses the individual height measurements from scenarios 2-5 and not the participants.

Protocol	Reporting & Analysis Plan	
Statistical Analysis Plan	Statistical Analysis Plan	Rationale for Changes

intranasal and/or systemic corticosteroids during the treatment period 5. Excluding subjects who have any of the above
 
Section 9.4.2.2: Adverse events (AEs) will be summarised for each study period (16-week single-blind baseline period, 52-week double-blind treatment period, and 8-week follow-up period) and displayed by treatment group. The onset date of the adverse events relative to the clinic visit dates will be used to determine in which period an adverse event occurs. Adverse events during the pre-treatment period include those with date of onset prior to study treatment initiation (first dose date). Adverse events during the on-treatment period include those with date of onset on or after the date of study treatment initiation and on or before the study treatment termination date. Adverse events during the post-treatment period include those with date of onset after the study treatment termination date.
 
Section 9.4.2.3: The number and percentage of subjects experiencing an exacerbation over the double-blind treatment period and the follow-up period will be summarised for each treatment group alongside the primary causes of the exacerbation.
	
5. Excluding height measurements for any of the above scenarios
 
Section 8.1: Adverse events (AEs) will be collected starting with the first administration of single-blind study treatment. Adverse events during the pre-treatment period include those with date of onset prior to study treatment initiation (first dose date). Adverse events during the on-treatment period include those with date of onset on or after the date of double-blind study treatment initiation and on or before the double-blind study treatment termination date. Adverse events during the post-treatment period include those with date of onset after the double-blind study treatment termination date.
 
Section 8.3: An exacerbation is defined as deterioration of asthma requiring the use of systemic corticosteroids (tablets, suspension, or injection) for at least 3 days or a single depot corticosteroid injection, or an in-patient hospitalisation or emergency department (ED) visit due to asthma that required systemic corticosteroids. Asthma exacerbations will not be recorded as an AE unless they meet the definition of an SAE. The incidence of exacerbations will be summarized by treatment group and listed.
	
The intention in the protocol was to summarise AEs relative to the treatment start date (i.e., pre-treatment, on-treatment and post-treatment), and not by study period (i.e., 16-week single-blind baseline period, 52-week double-blind treatment period, and 8-week follow-up period).
 
The protocol indicates that exacerbations will also be summarised for the FU period. Instead, we will summarise by phase (on-treatment and post-treatment).

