4.2. Treatment Arms and Duration

This study will be conducted over a total duration of approximately 76 weeks: 16-week run-in period, 52-week double-blind treatment period and 8-week follow-up period. The study randomisation will be stratified by country.

Eligible subjects will receive a single-blind placebo inhaler during the 16-week run-in period. After completing the run-in period, eligible subjects will be randomly allocated to one of two treatment regimens:

- inhaled FF 50 mcg administered OD in the morning for 52 weeks

or

- inhaled placebo administered OD in the morning for 52 weeks

Each treatment will be administered via the ELLIPTA dry powder inhaler [formerly referred to as a novel dry powder inhaler (NDPI)].

Subjects will also receive open-label montelukast (4 mg for subjects who are 5 years old and 5 mg for subjects who are ≥ 6 years old). Subjects will take one tablet of montelukast each evening for the duration of the study (from the run-in period through to the end of the follow-up period). **Note:** subjects who turn 6 years old during the study, will subsequently receive 5 mg of open-label montelukast.

In addition, each subject will receive a short acting beta 2 agonist (SABA) (i.e., albuterol/salbutamol [inhalation aerosol or nebuliser]) to be used as needed throughout the entire study period as rescue medication for symptomatic relief of asthma symptoms.

Subjects (i.e., the child) **must** attend the clinic on the following visits for spirometry and other key assessments:

- **Visits 1 and 3 (Screening visit and run-in period):**
 - Visit 1, subjects will attend the clinic for screening procedures. Subjects meeting the eligibility criteria will enter the 16-week run-in period.
 - Visit 3, subjects will attend the clinic for spirometry assessment and any other assessments as indicated in the Time and Events Table (Section 7.1).
- **Visit 5 (Randomisation):**
 - Eligible subjects will be randomised to one of two treatment groups.
 - Subjects will attend the clinic for spirometry assessments and any other assessments as indicated in the Time and Events Table (Section 7.1).
- **Visits 6, 7, 8, 9, 12, 15 and 18 (Double-blind treatment period)**
 - Subjects will attend the clinic for spirometry assessments and any other assessments as indicated in the Time and Events Table (Section 7.1).
- **Visit 20 (Follow-up period)**

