5.5. Withdrawal/Stopping Criteria

5.5.1. Subject Withdrawal by Investigator or Self-withdrawal

The following criteria will cause a subject to be discontinued from study treatment but every effort should be made to keep the subject in the study:

- 1. **Non-Compliance:** A subject is significantly non-compliant with the requirements of the protocol (see Section 6.7).
- 2. **Adverse Event:** A subject has an adverse event that, in the investigator's judgement, makes continued study treatment an unacceptable risk.

3. **Study Blinding Revealed:** The treatment blind is broken for any subject other than by GSK GCSP personnel.
4. If during the study the subject has a blood sample taken and the results meet the liver chemistry stopping criteria (see Section 5.5.3).
5. If during the study the subject has an ECG and the results meet the QTc stopping criteria (see Section 5.5.4).

In addition to the reasons above, a subject may be discontinued from study treatment at any time at the discretion of the investigator for safety, behavioural or administrative reasons.

If a subject discontinues study treatment, the subject will not automatically be considered as being withdrawn from the study but will be encouraged to stay in the study. An Early Treatment Discontinuation Visit should be conducted within approximately 24 hours of the subject stopping study medication (Section 7.1). In the event a subject discontinues study treatment at or during a scheduled visit, an Early Treatment Discontinuation Visit is not required; however, all study procedures scheduled at an Early Treatment Discontinuation Visit must be performed at this visit instead. These subjects will not be allowed to restart study treatment, however, will be asked to continue to follow the regular visit schedule (Section 7.1). Reasons for treatment discontinuation will be collected and, where possible, every effort will be made to collect growth measurements throughout the intended study period (with particular focus on obtaining the end of the 52-week treatment period height measurement) and recorded in the CRF as planned. After the Early Treatment Discontinuation Visit the subjects will no longer be required to complete the e-diary. The investigator should prescribe appropriate asthma medication to subjects who discontinue study treatment and elect to continue in the study. After treatment discontinuation, the prohibited medications listed in Section 6.10.2 are no longer applicable.

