9.4.2.2. Adverse Events

Regarding the safety assessment of inhaled FF 50 mcg, adverse events (incidence, type, severity) will be assessed throughout the study.

Adverse events (AEs) will be summarised for each study period (16-week single-blind baseline period, 52-week double-blind treatment period, and 8-week follow-up period) and displayed by treatment group. The onset date of the adverse events relative to the clinic visit dates will be used to determine in which period an adverse event occurs. Adverse events during the pre-treatment period include those with date of onset prior to study treatment initiation (first dose date). Adverse events during the on-treatment period include those with date of onset on or after the date of study treatment initiation and on or before the study treatment termination date. Adverse events during the post-treatment period include those with date of onset after the study treatment termination date.

The CRF text for AEs will be coded using the Medical Dictionary for Regulatory Activities (MedDRA) and will be reported using the primary System Organ Class (SOC) and Preferred Term (PT). The number of subjects with one or more events of any type will be calculated. Results will be displayed in the order of decreasing frequency, both across SOC and within SOC. A SOC will not be presented when the overall incidence for any adverse event within the particular system is 0. If the total incidence for any two or more adverse events is equal, the events will be presented in alphabetical order. Adverse events during each study period (baseline, treatment and follow-up) will also be listed, with SOC, event (preferred term), treatment group, number of subjects with the event, and specific subject numbers. Demographic details (e.g. age, gender and race), as well as details of the individual adverse events, will be included in these listings. Listings will be sorted within subject by the date of onset of the AE.

Similar summaries and listings will be provided for drug-related adverse events, and adverse events leading to withdrawal from study treatment.

Any deaths, pregnancies and serious adverse events (SAEs) reported during the study period will also be listed.

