9.4.2.3. Asthma Exacerbations

The number and percentage of subjects experiencing an exacerbation over the double-blind treatment period and the follow-up period will be summarised for each treatment group alongside the primary causes of the exacerbation.

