11.4.1.3. Study Phases for Asthma Exacerbations

Asthma exacerbations will be classified according to the time of occurrence relative to start and/or stop date of the double-blind study treatment.

Study Phase	Definition
Pre-Treatment	Exacerbation Onset Date \leq Start Date of Double-Blind Treatment - 1
On-Treatment	Start Date of Double-Blind Treatment \leq Exacerbation Onset Date \leq Stop Date of Double-Blind Treatment + 1
Post-Treatment	Exacerbation Onset Date \geq Stop Date of Double-Blind Treatment + 2

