where *Total Number of Inhalations Taken* is the total number of doses taken from all inhalers, *Expected Inhalations* is equal to 1 and *Start Date* and *Stop Date* are the earliest treatment start date and the latest treatment stop date recorded for all of the inhalers used in the calculation.

Participants who are either under- (<80%) or over- (>120%) compliant over the run-in and double-blind treatment periods according to both the diary card and the inhaler dose counter, will be identified. The numbers of these participants, as well as the number of participants whose compliance is unknown, will be summarized by treatment.

Extent of Exposure
 
 • Duration of exposure (days) to double-blind study treatment will be calculated as: 
 ○ Double-Blind Treatment Stop Date – Double-Blind Treatment Start Date + 1 • Participants who were randomised but did not report a double-blind treatment start/stop date, will have missing exposure. • Duration of post-treatment time (days) spent in the study will be calculated as: 
 ○ Study Conclusion Date – Double-Blind Treatment Stop Date • Duration of total time (days) spent in the study since first dose will be calculated as: 
 ○ Study Conclusion Date – Double-Blind Treatment Start Date + 1 • Double-blind treatment start and stop dates used will be the earliest (start) and latest (stop) of all dates recorded for the participant. Study conclusion is defined as completion or withdrawal, as applicable.

Concomitant Medications
 
 • Concomitant medications will be coded using the GSK Drug coding dictionary. Summaries of the number and percentage of participants taking concomitant medications will be displayed by ingredient without regard to Anatomical Therapeutic Chemical (ATC) classifications. These summaries will include single-ingredient medications and will present multi-ingredient medications according to the combination of the component ingredients. Summaries will be split into asthma and non-asthma concomitant medications, as well as into those taken pre-, on-, and post-treatment (as described in Section 11.4.1).

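### For exacerbations the SAP replaces the protocol's 52-week and 8-week windows with phases set by each child's stop date, and no safety incidence summary is specified per unit of time at risk

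*SAP*

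**What the plan says.** **Exacerbations, protocol.** Section 9.4.2.3 promises the number and percentage of children with an exacerbation "over the double-blind treatment period and the follow-up period will be summarised for each treatment group". Section 4.2 fixes the lengths: "16-week run-in period, 52-week double-blind treatment period and 8-week follow-up period".

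**Exacerbations, SAP.** Table 1 in 2.1 acknowledges the follow-up summary and replaces it: "Instead, we will summarise by phase (on-treatment and post-treatment"). Its rationale column states the change but gives no reason for it. Section 11.4.1.3 sets the phases: "Asthma exacerbations will be classified according to the time of occurrence relative to start and/or stop date of the double-blind study treatment". On-treatment runs from the first double-blind dose to the stop date + 1. Post-treatment starts at the stop date + 2 and has no stated end. Section 8.3 speaks only of incidence by treatment group. Table 2.56 shows the two phases separately, but its title confines it to the double-blind treatment period.

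**After early stopping.** Protocol 5.5.1 asks children who stop treatment to keep the regular visit schedule and tells the investigator to prescribe suitable asthma medication. It adds: "After treatment discontinuation, the prohibited medications listed in Section 6.10.2 are no longer applicable".

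**Adverse events.** Protocol 9.4.2.2 says "Adverse events (AEs) will be summarised for each study period", and in the same paragraph defines pre-, on- and post-treatment events by treatment dates. The SAP keeps only the treatment-date version and gives its reason in Table 1. SAP 8.1 and 8.2 report numbers and percentages. The risks plot (8.5, 11.6.4) uses ratios of simple proportions.

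**Time at risk.** SAP 11.6.2 derives double-blind exposure and also states "Duration of post-treatment time (days) spent in the study will be calculated as" study conclusion date minus stop date. Both are descriptive. No section uses either as a denominator.

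**The concern.** Incidence of adverse events and of exacerbations are the two endpoints of the secondary safety objective. A percentage is readily interpretable when everyone is observed for much the same time. The protocol's two exacerbation windows come close to that: they are common to all children and lose time only when a child leaves the study.

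Phases set by the stop date are not common to all. Two things follow.

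- The post-treatment summary mixes children observed for 8 weeks after a full year with children observed for most of a year after stopping early, possibly on other asthma medication. A reader who takes it as the follow-up result would be misled even if the arms stop equally.
- If one arm stops more often, it has less on-treatment time and more post-treatment time, so crude percentages differ between arms with no true difference in event rate.

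The exacerbation plan then contains no percentage by randomised arm over the common 52 weeks. The primary growth analysis, by contrast, follows a treatment-policy strategy (SAP 7.1.4).

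**Working it through.** The documents give no exacerbation rate, no adverse event rate and no stopping rate by arm, so there is no planned figure to reproduce. The nearest is the sample-size assumption of up to 10% stopping study medication within 12 weeks (protocol 9.2.1), which is not split by arm.

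**Step 1. Time at risk by phase.** From the documents: 52 weeks of treatment plus 8 of follow-up, 60 in all. A child who stops at week *w* and stays has *w* weeks on-treatment and 60 − *w* post-treatment (the one- or two-day offsets are ignored).

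| Stop week | On-treatment | Post-treatment | Ratio to completer's 8 weeks |
|---|---|---|---|
| 4 | 4 | 56 | 7.0 |
| 12 | 12 | 48 | 6.0 |
| 26 | 26 | 34 | 4.25 |
| 52 (completer) | 52 | 8 | 1.0 |

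Of the 48 weeks after a Week 12 stop, 40 lie inside the 52-week period.

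**Step 2. Percentage with an event.** Assumed: 0.3 events per child-year, constant and equal in both arms; a fraction *p* stops at week *w*; all are followed to Week 60. For *t* weeks at risk the chance of at least one event is 1 − exp(−0.3 × *t*/52):

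- 52 weeks: 25.92%; 26 weeks: 13.93%
- 8 weeks: 4.51%; 34 weeks: 17.81%

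With *w* = 26, *p* = 10% on FF and 20% on placebo:

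- Post-treatment, FF: 0.9 × 4.51 + 0.1 × 17.81 = 5.84%. Placebo: 0.8 × 4.51 + 0.2 × 17.81 = 7.17%. Ratio 0.81.
- On-treatment, FF: 0.9 × 25.92 + 0.1 × 13.93 = 24.72%. Placebo: 0.8 × 25.92 + 0.2 × 13.93 = 23.52%. Ratio 1.05.
- Mean weeks at risk, FF v placebo: 10.6 v 13.2 post-treatment, 49.4 v 46.8 on-treatment.

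**Step 3. Range.** With stopping at Week 12 instead, 10% v 20% gives 0.77 post-treatment and 1.09 on-treatment, and 10% v 30% gives 0.62 and 1.19. Across 0.1 to 0.6 events per year, stopping at Week 4 to 26, and FF v placebo stopping of 5% v 15%, 10% v 20% or 10% v 30%, the post-treatment ratio runs from 0.58 to 0.83 and the on-treatment ratio from 1.05 to 1.25. If FF stopped more often, the directions would reverse.

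**Step 4. Equal stopping.** With 10% stopping at Week 12 in both arms, both ratios are 1.00. The post-treatment figure is still 6.48%, against 4.51% over a true 8-week follow-up. Early stoppers contribute 0.1 × 24.19% = 2.42 points of it, or 37% of the children with a post-treatment event.

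**Step 5. The alternatives.** Under the same assumptions, events per person-year give a rate ratio of 1.00 in each phase. The protocol's windows give 25.9% over 52 weeks and 4.5% over follow-up in both arms.

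**Step 6. Definitions side by side.** Read literally, the Table 2.56 title excludes follow-up. A completer then has almost no post-treatment time and a Week 12 stopper has 40 weeks. Read with 11.4.1.3, the figures are 8 and 48. For adverse events, SAP 8.1 ends on-treatment at the stop date, while 11.4.2 ends it at the stop date + 1.

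**The case against.** Several stronger readings are tempting, and the documents do not support them.

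- *The SAP introduced treatment-date phases for adverse events.* It did not. Protocol 9.4.2.2 already had them, with no end limit, beside the study-period wording.
- *The on-treatment phase is open-ended.* It closes at stop + 1 and only varies in length.
- *Exacerbations will be reported as bare percentages.* SAP 8.3 says only incidence, and the shell for Table 2.56 is not shown. Rates are unspecified, not ruled out.
- *The protocol expects more placebo children to stop.* Section 4.4 says background montelukast should limit uncontrolled asthma on placebo and so limit drop-outs. That recognises a risk and describes its mitigation. Exacerbation is not a listed stopping criterion in 5.5.1, and Table 3 of the protocol keeps children who need limited steroid courses on treatment.

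The illustrated effect is also modest. With 225 per arm, 5.84% v 7.17% is about 13 v 16 children, and the standard error of the difference is about 2.3 points. No hypothesis is tested. The SAP's relative risks cover SAEs, withdrawals due to adverse events and AESIs, not exacerbations. Table 1.32, the Kaplan-Meier plots and the listings would let a careful reader see unequal stopping. The protocol itself asks for percentages, not rates, and its windows are also shortened for children who leave the study.

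All of this stands, and it limits the point. It does not restore the dropped exacerbation summary, make the post-treatment phase equivalent to the follow-up, or supply a denominator. The distortion is systematic, so the size of the sampling error does not remove it.

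**Conclusion.** The point holds in limited form. For exacerbations, the SAP gives up a summary over windows common to all children for one whose length depends on when each child stopped. The mixing of 8-week and much longer observation needs only that some children stop early and stay. Distortion between arms needs unequal stopping, which is foreseeable but nowhere stated. Under the assumed 0.3 events per year and 10% v 20% stopping at Week 26 it is about 0.81 post-treatment and 1.05 on-treatment. The direction cannot be known in advance, so it should not be said that the plan favours or penalises FF.

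For adverse events and AESIs the point is narrower: crude proportions and crude relative risks, with no person-time beside them. Table 2.56 and the end of the on-treatment phase need clarifying in either case. The point concerns secondary safety reporting. Sample size and the primary growth analysis are unaffected.

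**What to change.** 1. Beside the phase summary, keep the protocol's number and percentage of children with an exacerbation, by randomised arm, for Visit 5 to Visit 18 and for Visit 18 to Visit 20, regardless of treatment status. This comparison preserves randomisation.
2. Add exposure-adjusted rates per person-time to the on- and post-treatment summaries of AEs, SAEs, AESIs and exacerbations, using the 11.6.2 durations. Leave the pre-treatment and coding tables alone. Align the day counts: with phases split at stop + 1 and stop + 2, on-treatment time is the 11.6.2 exposure plus one day, and post-treatment time is the 11.6.2 figure minus one day. Rates correct for length of observation, not for which children stop, so they supplement item 1 and do not replace it.
3. Split post-treatment exacerbations at Visit 18, into those inside the 52-week period after an early stop and those in follow-up.
4. Reconcile the Table 2.56 title with the unbounded phase in 11.4.1.3, and the end of on-treatment for adverse events in 8.1 with 11.4.2.

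The cost is SAP wording and a few extra columns. No new data are needed.
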